### 3. DELIVERABLES FROM IQVIA CLINICAL MONITORING/PROJECT MANAGEMENT

Any protocol deviations will be recorded in the CTMS and the Project Manager is to provide the 'Protocol Deviations' log, as a report from this system. In addition, clinical inspection reports and quality assurance (QA) site issues are to be provided, if applicable. These documents, if applicable, should be available at the time of the DR. It should be noted that if any Good Clinical Practice (GCP) issues are identified at specific sites, this information should be communicated to the IQVIA STL for documentation and discussion at the DR meeting.

### 4. DELIVERABLES FROM IQVIA BIOSTATISTICS

The following deliverables are to be provided by the IQVIA Biostatistics:

- Guidelines for the population assignment and DR Plan as Appendix to the SAP.
- MS/EXCEL dataset for the prior and concomitant medications (CRITERION [5]) as well as for the previous or concurrent prohibited medical conditions (CRITERION [6]), to IQVIA Medical Monitor (see Appendix 4 section 4.1.3.2 and 4.1.3.3)
- Specific DR listings (Protocol deviation [CTMS log], programmed deviations listing, population assignment and Visit windowing) (MS/WORD document and/or MS/EXCEL spreadsheet, as appropriate).
- Population assignment and major protocol deviations will be provided in an MS/EXCEL spreadsheet.
- Following the DR meeting the population assignment and major protocol deviations signature page for authorising.

---

Document: ATX\_GD\_59 Final 1.0 SAP 28FEB2018.docx  
Author: [name]

Version Number: Final 1.0  
Version Date: 28FEB2018

Template No: CS\_TP\_BS016 Revision 4  
Effective Date: 01Apr2016

Reference: CS\_WI\_BS005

Copyright © 2009, 2010, 2012, 2016 Quintiles Transnational Corp. All rights reserved.  
The contents of this document are confidential and proprietary to Quintiles Transnational Corp. Unauthorized use, disclosure or reproduction is strictly prohibited.

## 4.1. IDENTIFICATION OF THE POPULATIONS AND MAJOR PROTOCOL DEVIATIONS

This section contains a detailed description of the criteria which are to be used in the definition of the populations and in the testing of subject validity for the various populations. The criteria to be used to define a valid course and potential protocol deviations are also defined in this section.

All potential protocol deviations are to be summarised in the MS/EXCEL spreadsheet. This MS/EXCEL spreadsheet is to provide a by-subject summary of each subject's validity together with all of his/her potential protocol deviations.

The following populations are defined for presentation of the safety and efficacy analysis:

### 4.1.1. STUDY POPULATION

The Study population corresponds to all enrolled subjects, i.e. all subjects eligible for enrolment into the study at the Screening visit.

Exclusion criteria from the study population:

4.1.1.1. Subjects who did not provide written informed consent prior to any specific study-related procedures.

**CRITERION [1]:** No Written Informed Consent.

**FIXED CATEGORY:** Inclusion and Exclusion Criteria.

**DEVIATION STATUS:** Major.

**Note:**

The criteria related to informed consent to be met by each subject to be assessed are:

Term/Description	Inclusion and Exclusion Criteria (as Recorded on the eCRF and Verified)
The subject must be willing and able to give written informed consent and must be willing to comply with protocol assessments/procedures.	Inclusion 6
Verify informed consent date collected on the eCRF to establish whether or not consent was provided prior to performing any study-related procedures and whether or not the subject was eligible for enrolment in the study in accordance with the clinical study protocol's specified inclusion and exclusion criteria.	Verify inclusion 6

#### 4.1.2. INTENTION-TO-TREAT [ITT]/SAFETY POPULATION

An ITT population will be defined for use in presenting baseline, efficacy and safety data. The ITT population corresponds to all subjects who received at least one administration of study drug at any time+ during the study, irrespective of compliance with eligibility and other protocol criteria.

The ITT population set is regarded as primary for the safety analyses.

Exclusion criteria from the ITT population:

4.1.2.1. Subjects who did not receive a dose of study drug or part thereof.

**CRITERION [2]:** No Study Drug Administered.

**FIXED CATEGORY:** Treatment Schedule.

**DEVIATION STATUS:** Major.

Document: ATX\_GD\_59 Final 1.0 SAP 28FEB2018.docx  
 Author: [name]

Version Number: Final 1.0  
 Version Date: 28FEB2018

Template No: CS\_TP\_BS016 Revision 4  
 Effective Date: 01Apr2016

Reference: CS\_WI\_BS005

Copyright © 2009, 2010, 2012, 2016 Quintiles Transnational Corp. All rights reserved.  
 The contents of this document are confidential and proprietary to Quintiles Transnational Corp. Unauthorized use, disclosure or reproduction is strictly prohibited.

#### 4.1.3. PER-PROTOCOL [PP] POPULATION

The PP population to include all subjects considered valid for the ITT population with no identified major protocol deviations as reviewed and confirmed by Apitope prior to analysis.

Major protocol deviations are defined as any factor affecting the efficacy outcome or the treatment of the subject.

The PP population is further defined by the following valid course criteria (ICH-E9):

- Overall treatment compliance, i.e. subjects that did not receive the full treatment regimen.
- Eligible in accordance with the clinical study protocol's specified inclusion and exclusion criteria.
- Specifically criteria which could affect the efficacy outcome or the treatment of the subject:
  - Not taken prohibited medications during the treatment period.
  - Presence of prohibited medical conditions.
  - Not received anti-thyroid drugs prior to week 22.

Exclusion criterion from the PP population:

- All subjects excluded from the ITT population.
- Overall treatment non-compliance.

For each subject included in the PP population, the compliance with regards to the administration of the single dose of study drug is to be assessed as a binary outcome:

- Yes: All doses received and at least 80% of protocol-specified total study drug dose ( $\mu\text{g}$ ) injected for the entire treatment period.
- No: Not all doses received or not at least 80% of protocol-specified total study drug dose ( $\mu\text{g}$ ) injected for the entire treatment period

**CRITERION [3]:** Non-compliance with Study Drug Administration.

FIXED CATEGORY: Treatment Schedule.

DEVIATION STATUS: Major/Minor to be decided on a case-by-case basis at the DR meeting.

---

Document: ATX\_GD\_59 Final 1.0 SAP 28FEB2018.docx  
Author: [name]

Version Number: Final 1.0  
Version Date: 28FEB2018

Template No: CS\_TP\_BS016 Revision 4  
Effective Date: 01Apr2016

Reference: CS\_WI\_BS005

Copyright © 2009, 2010, 2012, 2016 Quintiles Transnational Corp. All rights reserved.  
The contents of this document are confidential and proprietary to Quintiles Transnational Corp. Unauthorized use, disclosure or reproduction is strictly prohibited.

**Notes:**

Compliance of study drug administration is to be evaluated with regards to the number of injections and the amount of dose received. Each factor is formulated as a question with a binary response, either 'Yes' or 'No'.

The factors to be evaluated are as follows:

- All 10 doses received, that is 100% compliance to number of doses received. Major
- At least 80% of protocol-specified total study drug dose amount injected (Yes/No). Major.

Dose Compliance (%) = (Amount (μg) of drug injected / Protocol-specified drug amount (μg))\*100

#### 4.1.3.1. Met all Inclusion and none of the Exclusion Criterion

The inclusion criteria and exclusion criteria are presented in section 8 of the clinical study protocol. For each criterion, as appropriate, a response of 'Yes/No' is to be obtained at Screening. The aforementioned inclusion criteria and exclusion criteria responses are recorded in the eCRF.

**CRITERION [4]:** Eligibility Criteria Not Met.

FIXED CATEGORY: Inclusion and Exclusion Criteria.

DEVIATION STATUS: Major/Minor to be decided on a case-by-case basis at the DR meeting.

#### 4.1.3.2. Subjects who used Prohibited Prior/Concomitant Medications (including anti-thyroid drugs before Week 22 visit)

**CRITERION [5.1]:** Use of Prohibited Prior/Concomitant Medications.

FIXED CATEGORY: Concomitant Medications.

DEVIATION STATUS: Major/Minor to be decided on a case-by-case basis (in collaboration with the IQVIA Medical Advisor) at the DR meeting.

---

Document: ATX\_GD\_59 Final 1.0 SAP 28FEB2018.docx  
Author: [name]

Version Number: Final 1.0  
Version Date: 28FEB2018

Template No: CS\_TP\_BS016 Revision 4  
Effective Date: 01Apr2016

Reference: CS\_WI\_BS005

Copyright © 2009, 2010, 2012, 2016 Quintiles Transnational Corp. All rights reserved.  
The contents of this document are confidential and proprietary to Quintiles Transnational Corp. Unauthorized use, disclosure or reproduction is strictly prohibited.

**CRITERION [5.2]:** Received Anti-thyroid Drugs prior to Week 22.

FIXED CATEGORY: Concomitant Medications.

DEVIATION STATUS: Major deviation.

**Note:**

All prior/concomitant medications are to be reviewed on a by-subject basis by the IQVIA Medical Advisor in order to identify the use of any prohibited prior/concomitant medication as specified in the protocol. The prohibited prior/concomitant medications identified by the IQVIA Medical Advisor are to be flagged in the DR listing as well as anti-thyroid drugs flagged programmatically for ease of review in inclusion in the summary excel document.

The duration (days) since the use of the prohibited prior/concomitant medication is calculated as follows:

- Duration (days) = (Start date of prior/concomitant medication – Date of first study drug administration) +1.

#### 4.1.3.3. Subjects who have Previous or Concurrent Prohibited Medical Conditions

**CRITERION [6]:** Previous or Concurrent Prohibited Medical Conditions

FIXED CATEGORY: Medical History.

DEVIATION STATUS: Major/Minor to be decided on a case-by-case basis (in collaboration with the Medical Advisor) at the DR meeting.

**Note:**

All medical histories are to be reviewed on a by-subject basis by the IQVIA Medical Advisor in order to identify prohibited medical conditions. The prohibited medical conditions identified by the IQVIA Medical Advisor are to be flagged in the relevant MS/EXCEL document and sent back to the IQVIA STL for inclusion in the population and protocol deviation summary (MS/EXCEL document).

The effect of the possible deviation will be determined as Major/Minor during the DR meeting.

---

Document: ATX\_GD\_59 Final 1.0 SAP 28FEB2018.docx  
Author: [name]

Version Number: Final 1.0  
Version Date: 28FEB2018

Template No: CS\_TP\_BS016 Revision 4  
Effective Date: 01Apr2016

Reference: CS\_WI\_BS005

Copyright © 2009, 2010, 2012, 2016 Quintiles Transnational Corp. All rights reserved.  
The contents of this document are confidential and proprietary to Quintiles Transnational Corp. Unauthorized use, disclosure or reproduction is strictly prohibited.

#### 4.1.4. ANTI-THYROID DRUG POPULATION

The anti-thyroid drug population is defined as any ITT subject taking anti-thyroid drugs at any time post first dose of ATX-GD-59 up to the Week 22 visit.

Exclusion criterion from the anti-thyroid drug population:

- All subjects excluded from the ITT population.
- All subjects not taking anti-thyroid drugs at any time post first dose of ATX-GD-59 to the Week 22 visit.

**CRITERION [7]:** Did not Receive Anti-thyroid Drugs prior to Week 22.

FIXED CATEGORY: Concomitant Medications.

STATUS: Yes/No

## 4.2. SUBJECTS WHO DID NOT ADHERE TO THE VISIT SCHEDULE.

**CRITERION [8]:** Non-adherence to Visit Schedule.

FIXED CATEGORY: Assessment Schedule.

DEVIATION STATUS: Major/Minor to be decided on a case-by-case basis at the DR meeting.

**Note:**

Only scheduled visits adherence applicable to the study is to be validated according to the relevant visit window below. Visits not in accordance with the table below are to be identified by means of a flag on the listing of study visits:

---

Document: ATX\_GD\_59 Final 1.0 SAP 28FEB2018.docx  
Author: [name]

Version Number: Final 1.0  
Version Date: 28FEB2018

Template No: CS\_TP\_BS016 Revision 4  
Effective Date: 01Apr2016

Reference: CS\_WI\_BS005

Copyright © 2009, 2010, 2012, 2016 Quintiles Transnational Corp. All rights reserved.  
The contents of this document are confidential and proprietary to Quintiles Transnational Corp. Unauthorized use, disclosure or reproduction is strictly prohibited.

Visit	Protocol Study Day	Deviation if outside	Visit Window relative to date of first study drug administration
Screening visit (Week -4: )	Day -28 to -1	+ 5 days	Week -4: Day -33 to Day -1
Study day 1 visit	1	Not applicable	
Dose titration period visits	Week 2: Day 14 Week 4: Day 28 Week 6: Day 42 Week 8: Day 56	± 3 days	Week 2: Day 11 to 17 Week 4: Day 25 to 31 Week 6: Day 39 to 45 Week 8: Day 53 to 59
Full dose Treatment visits	Week 10: Day 70 Week 12: Day 84 Week 14: Day 98 Week 16: Day 112 Week 18: Day 126	± 3 days	Week 10: Day 67 to 73 Week 12: Day 81 to 87 Week 14: Day 95 to 101 Week 16: Day 109 to 115 Week 18: Day 123 to 129
Follow-up visits (Week 22)	Week 22: Day 154	± 3 days,	Week 22: Day 151 to 157
Follow-up visits (Week 30)	Week 30: Day 210	± 7 days	Week 30: Day 203 to 217

Study day is calculated relative to the date of first administration of study drug and is only presented for subjects with a study drug administration date (see section 6.1 ).

The ET visit will be allocated to a scheduled visit according to the table above, where the ET visit has occurred in place of the scheduled visit and is within the relevant visit window. Any ET visits will be reviewed for allocation to a scheduled visit, at the DR meeting.

Document: ATX\_GD\_59 Final 1.0 SAP 28FEB2018.docx  
Author: [name]

Version Number: Final 1.0  
Version Date: 28FEB2018

Template No: CS\_TP\_BS016 Revision 4  
Effective Date: 01Apr2016

Reference: CS\_WI\_BS005

Copyright © 2009, 2010, 2012, 2016 Quintiles Transnational Corp. All rights reserved.  
The contents of this document are confidential and proprietary to Quintiles Transnational Corp. Unauthorized use, disclosure or reproduction is strictly prohibited.

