1 SUMMARY/SYNOPSIS

Title of Study:	Safety and proof of principle study of ATX-GD-59 in male and female subjects with Graves' disease not currently treated with anti-thyroid therapy: An Open label study, with an upward titration over five dose levels administered by Intradermal injection.
Countries:	United Kingdom
Phase of development:	Phase I
Study Objectives:	

PRIMARY
 
 • To evaluate whether ATX-GD-59 administration every two weeks by intradermal injection is safe and well tolerated in male and female subjects with Graves' disease, not currently treated with anti-thyroid therapy. 	

SECONDARY
 
 • To assess the effects of ATX-GD-59 on TSHR antibody levels. • To assess the ratio of stimulatory vs inhibitory TSHR antibodies. • To assess the effect of ATX-GD-59 on free T3, free T4 and TSH serum levels. 	

EXPLORATORY
 
 • To assess the effects of ATX-GD-59 on TSHR induced Peripheral Blood Mononuclear Cell (PBMC) T cell activity. • To assess the effects of ATX-GD-59 on the T cell cytokine signature. • To assess the effects of ATX-GD-59 IL-10 pathway and associated genes (mRNA). 	
Methodology:	

This will be an open label, ascending dose evaluation of the safety, tolerability and efficacy of ATX-GD-59 in approximately 12 evaluable subjects with Graves' disease who are HLA-DRB1*15, HLA-DRB1*03 and/or HLA-DRB1*04 positive and not currently treated with anti-thyroid therapy.
 
The first four subjects will be recruited sequentially with a minimum of 48 hours between the first dose of each subject. Individual subject safety data will be reviewed by the Investigator and the Sponsor or Sponsor's representative after the first dose of ATX-GD-59. Dosing of the remaining subjects will only commence once the first subject has received the second dose and there are no safety concerns identified.
 
There will be an upward titration over five dose levels (injection(s) of 25, 50, 100, 400 and 800 µg) of ATX-GD-59 followed by injection(s) of 800 µg injected on five further occasions. All doses are based on the total peptide.
 
All doses will be administered by intradermal injection at intervals of 14 +/- 3 days.
 
An estimated 33 subjects will be screened, with approximately 15 subjects receiving at least one dose of ATX-GD-59.
	

Number of Subjects: Approximately 12 subjects to complete dosing and attend the Week 22 visit.
	

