## 4. STUDY DESIGN

### 4.1. GENERAL DESCRIPTION

This is a phase I, first in human, open-label within subject dose-escalating study to evaluate the safety and efficacy of ATX-GD-59 in approximately 12 evaluable subjects with Graves' disease who are HLA-DRB1\*15, HLA-DRB1\*03 and/or HLA-DRB1\*04 positive and not currently treated with anti-thyroid therapy.

There will be an upward titration over five dose levels (injection(s) of 25, 50, 100, 400 and 800 µg) of ATX-GD-59, followed by a further five injections of the highest dose (expected to be 800 µg total peptide). All doses are based on the total peptide.

No control group will be utilized in this study and all subjects will receive the same dose-escalation schedule of ATX-GD-59.

All doses will be administered by intradermal injection to the anterior abdominal wall or thigh at intervals of 14 +/- 3 days.

---

Document: ATX\_GD\_59 Final 1.0 SAP 28FEB2018.docx  
Author: [name]

Version Number: Final 1.0  
Version Date: 28FEB2018

Template No: CS\_TP\_BS016 Revision 4  
Effective Date: 01Apr2016

Reference: CS\_WI\_BS005

Copyright © 2009, 2010, 2012, 2016 Quintiles Transnational Corp. All rights reserved.  
The contents of this document are confidential and proprietary to Quintiles Transnational Corp. Unauthorized use, disclosure or reproduction is strictly prohibited.

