## 6. GENERAL CONSIDERATIONS

### 6.1. REFERENCE START DATE AND STUDY DAY

Study Day will be calculated from the reference start date, and will be used to present start/ stop day of assessments and study events relative to the reference start date.

Reference start date is defined as the first administration date of study drug (Study Day 1).

- If the date of the assessment/event is on or after the reference start date then:

Study Day = (date of assessment/event – reference start date) + 1.

- If the date of the assessment/event is prior to the reference start date then:

Study Day = (date of assessment/event – reference start date).

In the situation where the assessment/event date is partial or missing, Study Day, and any corresponding durations will appear missing in the listings.

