## 9. DISPOSITION AND WITHDRAWALS

Protocol deviations are recorded by the monitor in CTMS throughout the study. Disposition information is captured on the ET and End of Study eCRF.

All subjects who provide informed consent will be accounted for in this study.

The following summaries will be provided:

- Incidence of subjects enrolled, screen failures including the initial screen for re-screened subjects, treated, completed study treatment, early discontinuation of treatment, completed study, early withdrawal from study participation including the primary reasons for early discontinuation from treatment and withdrawal from study.
- Analysis populations.

The following data will be presented in by-subject listings:

- Study disposition details including last dose received (and whether titration or full treatment dose) prior to completion/early discontinuation from treatment or from the study (All subjects). Note screening failures will be flagged in the listing
- Protocol deviations. All protocol deviations recorded by the monitor in CTMS throughout the study (site-level and subject-level) (Study population).
- Study visits including protocol and actual study day, deviation, flagging of any outside protocol-specified windows as well as ET visit assignments to a scheduled visit (ITT population).
- Analysis population assignments including reason(s) for exclusion from the PP population. Note that all efficacy listings will also include analysis population membership flags. Major protocol deviations identified during the study by the monitor and protocol deviations determined during analysis and reporting of the study data will be included in the reason(s) for exclusion (Study population).
- Eligibility criteria, including inclusion and exclusion criteria exceptions and eligibility verification (All Subjects). Note screening failures will be flagged in the listing.

The following deviation will apply for the visit listing:

- Deviation = Protocol Study Day – Actual Study Day.

---

Document: ATX\_GD\_59 Final 1.0 SAP 28FEB2018.docx  
Author: [name]

Version Number: Final 1.0  
Version Date: 28FEB2018

Template No: CS\_TP\_BS016 Revision 4  
Effective Date: 01Apr2016

Reference: CS\_WI\_BS005

Copyright © 2009, 2010, 2012, 2016 Quintiles Transnational Corp. All rights reserved.  
The contents of this document are confidential and proprietary to Quintiles Transnational Corp. Unauthorized use, disclosure or reproduction is strictly prohibited.

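### SAP Appendix 4 lists post-Day 1 visits as elapsed days, one below the SAP's own study day; separately, its time-since-use formula for prohibited medication runs from the start date

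*SAP*

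**What the plan says.** SAP section 6.1 makes the date of first dose Study Day 1. For dates on or after it the rule is "Study Day = (date of assessment/event – reference start date) + 1". For earlier dates the plain difference is used, so there is no Day 0.

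The table in SAP Appendix 4, section 4.2 has a column titled Protocol Study Day. The first-dose visit is 1. The titration visits are "Week 2: Day 14 Week 4: Day 28 Week 6: Day 42 Week 8: Day 56", and the series continues in steps of 14 to Day 126 at Week 18, then Day 154 at Week 22 and Day 210 at Week 30. Windows are +/-3 days around these values (+/-7 at Week 30). The note below the table says that study day "is only presented for subjects with a study drug administration date (see section 6.1", which points to the definition above. Early termination (ET) visits are allocated to scheduled visits from this table.

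SAP section 9 defines, for the visit listing, "Deviation = Protocol Study Day – Actual Study Day". That listing carries the out-of-window flags "as well as ET visit assignments to a scheduled visit (ITT population", so it covers all dosed subjects.

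SAP Appendix 4, section 4.1.3.2 defines a variable labelled as days since use of a prohibited medication. It is the medication's start date minus the first-dose date, plus 1. The stop date is not used, and the +1 applies before and after first dose alike.

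**The concern.** The table and the definition that it cites count differently. A programmer who takes actual study day from section 6.1 and compares it with the table is subtracting two scales that differ by one day. The listed deviation is then wrong by a day at every post-Day 1 visit, and each window is shifted. The flags feed criterion [8], which the data review meeting considers when it settles per-protocol membership. The same windows help to decide whether an ET visit enters a summary table in place of a scheduled visit (SAP section 6.4).

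The medication variable is a different kind of problem. Exclusion criteria 3, 7, 14 and 15 look back three months from Study Day 1, so what matters is when use ended. A figure built on the start date does not tell the meeting that.

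**Working it through.** **Inputs.** Section 6.1: study day = elapsed days + 1 on or after first dose. Appendix 4, section 4.2: tabled days and windows. Section 9: deviation = tabled day - actual study day.

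**Step 1: reproduce the table.** As elapsed days (7 x week), all 11 post-Day 1 entries are reproduced. As section 6.1 study days (7 x week + 1), none is.

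| Week | Tabled day | Section 6.1 day | Deviation if on time |
|---|---|---|---|
| 2 | 14 | 15 | -1 |
| 4 | 28 | 29 | -1 |
| 6 | 42 | 43 | -1 |
| 8 | 56 | 57 | -1 |
| 10 | 70 | 71 | -1 |
| 12 | 84 | 85 | -1 |
| 14 | 98 | 99 | -1 |
| 16 | 112 | 113 | -1 |
| 18 | 126 | 127 | -1 |
| 22 | 154 | 155 | -1 |
| 30 | 210 | 211 | -1 |

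Because the formula subtracts actual from planned, -1 reads as one day late.

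**Step 2: windows.** Week 2 is tabled as Day 11 to 17. As section 6.1 study days these are 10 to 16 elapsed days, or -4 to +2 around 14. The same shift holds for every visit to Week 22, although SAP section 4.3.5 also gives the Week 22 window as +/-3. Week 30 is tabled as Day 203 to 217, or 202 to 216 elapsed days, which is -8 to +6 around 210.

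**Step 3: boundary cases at Week 2.** SAP section 4.1 has dosing "at intervals of 14 +/- 3 days", so 11 to 17 days after first dose is in range.

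- 17 days after first dose is Study Day 18: flagged, though within tolerance.
- 10 days after first dose is Study Day 11: accepted, though outside tolerance.

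At each visit only two elapsed days are misclassified: +3 and -4 (at Week 30, +7 and -8).

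**Step 4: how many entries.** The protocol synopsis expects about 33 screened, "with approximately 15 subjects receiving at least one dose of ATX-GD-59". If all 15 attended all 11 later visits, 15 x 11 = 165 listed deviations would be one day off. For 12 completers the figure is 12 x 11 = 132. Withdrawals lower the 165, so it is an upper bound. Wrong flags cannot be counted from the documents: there are none if no visit falls on the two affected days, and in the extreme every attended visit is affected. Planned numbers imply about 15 - 12 = 3 dosed non-completers, so few ET visits are exposed.

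**Step 5: the medication formula.** Take two courses that both started 200 days before first dose, one stopped 150 days before and the other 30 days before. Both give -200 + 1 = -199, although only the second reaches into a three-month look-back. A start one day before first dose gives -1 + 1 = 0, where section 6.1 gives -1. Starts on or after first dose agree with section 6.1.

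**The case against.** The best defence is that the window column is expressed relative to the date of first dose, so the days are simply elapsed days. Read that way the windows are exactly +/-3 and +/-7. But on an elapsed scale the first-dose row would be 0, not 1; the note cites section 6.1; and section 9 subtracts an actual study day for which section 6.1 is the SAP's only definition. What stands is that the numbers are sound as elapsed days, so relabelling is a sufficient repair. It may be the better one if protocol sections not available here print the same days.

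A second defence is that a constant -1 would be noticed at the data review meeting. That is plausible for the deviations, less so for a yes/no flag on a boundary day.

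A third is that safeguards limit the effect, and this stands in full. By-visit summaries use nominal visits (SAP sections 6.4 and 6.5). ET visits are reviewed one by one. Criteria [5.1] and [8] are graded case by case. For medications, no threshold is applied to the variable, eligibility is also checked under criterion [4], and the medical advisor reviews every subject's medications.

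A reader might also infer that using the start date contradicts section 6.1. It does not: section 6.1 does not say which medication date to use. The start date is a mismatch between label and content; only the +1 before first dose conflicts with section 6.1.

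**Conclusion.** The point holds and is minor. All 11 post-Day 1 visit days are one below the study day that the table itself cites. Followed literally, the rules list -1 for each on-time visit and shift each window one day early. This rests on the actual day being computed by section 6.1, as section 9 and the table note imply.

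A reader might infer that every listed deviation is wrong, that per-protocol membership changes, or that efficacy results are affected. The documents do not support this. The Study Day 1 row is correct and the screening row fits either convention. Neither criterion [5.1] nor criterion [8] removes anyone automatically. The only route to a summary table is an ET visit that falls on a boundary day.

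The medication formula is a separate and smaller defect. It puts a mislabelled auxiliary figure before the data review meeting, and no decision is shown to depend on it.

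**What to change.** **Visit table.** Use one convention for the table, the flags, ET allocation and the section 9 deviation. Either:

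- add 1 to each post-Day 1 nominal day and window limit, giving nominal days 15, 29, 43, 57, 71, 85, 99, 113, 127, 155 and 211 (for example Week 2: 12 to 18; Week 30: 204 to 218); or
- keep the numbers, label them days since first dose, and compute the actual day and the deviation without the +1.

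**Medication variable.** Relabel the existing value as the medication start day and compute it by section 6.1. For medications with a complete stop date before first dose, add first-dose date minus stop date. Otherwise show the recorded stop date or that use is ongoing. List no imputed durations: for partial dates section 6.1 already says that "Study Day, and any corresponding durations will appear missing in the listings", and Appendix 2 keeps imputed dates out of listings.

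The cost is one table edited or relabelled, one variable relabelled and one simple difference added. The dates needed are already collected.
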